5.1 Number of Subjects, Duration, and Number of Investigational Devices

This study will involve up to 75 subjects implanted with the study device among all active sites. As not all patients consented for evaluation will go forward to implantation, the number of subjects consented for the study is expected to be higher (up to 150). No site will implant more than 15 subjects without prior authorization from Medtronic in order to minimize bias.

Subjects will be consented for follow-up through five years following implantation, and all implanted subjects will be followed per protocol through five years following implantation. Subjects who exit from the study after implantation will not be replaced. The enrollment period is estimated to be between 9 and 20 months, and the estimated total study duration (first subject implanted to last subject completing his/her last follow-up exam) is estimated to be seven years.

The number of investigational TAVR systems involved in this study is estimated to be between 75 and 150 (inclusive of devices used during index implantation procedures, devices opened but not used, and devices shipped to sites as inventory for the study but not opened or used).

5.2 Rationale

The safety and effectiveness of the Medtronic self-expanding Evolut R and PRO TAVR systems have been established through rigorous clinical evaluation in patients with severe symptomatic AS. However, contemporary evidence from scientific literature indicates patients with a degree of AS outside of the current TAVR indications are also at risk for serious adverse effects of AS. The risk and benefits of TAVR in patients with severe asymptomatic AS has not been well studied in prospective clinical studies, although clinical trials have recently been initiated in AS patients using the balloon expandable TAVR system.

This feasibility study is intended to obtain initial procedural safety and efficacy data on the use of the Medtronic self-expanding Evolut PRO+ TAVR system in this group of AS patients. Data from this study will be used to inform the design of future pivotal studies to expand the current indications to include this population. Specifically, the study objectives and associated endpoints are intended to fully characterize the spectrum of AS severity, LV function, and symptomology, provide information on event rates for pivotal sample size estimations, and refine the entrance criteria for future pivotal studies. The single arm design and sample size of 75 subjects is consistent with the views and opinions of US FDA physicians regarding feasibility studies in the development of percutaneous heart valves⁵⁵ and will provide adequate information to inform a pivotal study. A comprehensive bench testing protocol has been completed on the Evolut PRO+ system and is generalizable to the study population. The clinical study endpoints are relevant and consistent with the study objectives. The design of this study is based on clinical evaluation and aligned with risk assessment results.

5.3 Centers for Medicare Services Considerations (United States Centers only)

This study protocol is designed to ensure all beneficiaries of the United States Centers for Medicare Services (CMS) are eligible for participation, and that the results are generalizable to all beneficiaries

with the degree of AS and symptomology under investigation. Specifically, the inclusion/exclusion criteria require that the subjects to be ≥ 65 years of age, anatomically suited for the study TAVR system, and have a degree of AS that places them at risk for adverse cardiac events from their AS.

An analysis of 2018 US claims data for claims with a diagnosis of nonrheumatic aortic stenosis found that 88% of patients were age 65 or older, and Medicare was the primary payer in 84% of the claims, and secondary payer in 88% of the claims.⁵⁶ Therefore, results from this study will be generalizable to the Medicare population. In addition, the inclusion and exclusion criteria ensure that traditionally underrepresented groups (e.g. minorities, women) will not be excluded from this study. Information on subject age, gender, and ethnicity will be collected in the study through electronic Case Report Forms (eCRFs).

In addition, investigational sites are expected to retain participation of all enrolled subjects through their routine processes for arranging follow-up visits and encouraging subjects to attend visits and continue his/her participation. Finally, the study report will include information (e.g. % of subjects by race, gender) on the level of representation of these traditionally underrepresented groups among the overall study population.

5.4 Investigational Sites

This study may be conducted at up to 25 sites in the United States, Canada, Europe, Israel, Australia, and New Zealand. Investigative sites will meet the following criteria:

1. The site will have extensive experience with TAVR and SAVR, including the following:
 - Interventional Cardiologist with ≥ 20 TAVR procedures in the prior year, or ≥ 40 TAVR procedures in the prior two years.
2. The site will have the presence or capacity of establishing an investigative team consisting of the following:
 - Interventional Cardiologist with expertise in transcatheter aortic valve replacement
 - Cardiothoracic Surgeon with expertise in aortic valve replacement
 - Echocardiographer with expertise in evaluation of aortic stenosis and speckle-tracking echocardiography (STE), dobutamine stress echocardiography, and prosthetic valve evaluation
 - Cardiovascular Imaging Specialist (either radiologist or cardiologist) with expertise in multi-detector computed tomography (MDCT) for pre-TAVR procedure planning and cardiac MRI
 - Exercise Testing physician with expertise in exercise tolerance testing
 - Study Coordinator with experience in regulated medical device studies

5.5 Site Study Team Members

The following is a description of the key personnel who will form the investigative team at each site.

5.5.1 Site Principal Investigator

Each site will have a Principal Investigator (PI) who is either an interventional cardiologist, cardiothoracic surgeon, or non-interventional cardiologist. The PI has overall responsibility for the conduct of the study at the site, including protecting the rights, safety, and welfare of the study subjects at their site, the integrity of the study data generated by their site, and for ensuring the study is conducted in compliance with the Clinical Investigation Plan, all relevant regulatory requirements, and the IRB/EC requirements. The site PI may also serve as a member of the Heart Team.

5.5.2 Heart Team

Each site will utilize a local multi-disciplinary Heart Team to assess and document eligibility of the prospective subject for the study. Local Heart Team members must be trained, delegated, and activated to participate in the clinical study. At a minimum, the local Heart Team should include the following four members:

1. A Cardiothoracic Surgeon
2. An Interventional Cardiologist
3. An Echocardiographer

5.5.3 Echocardiographer

Each site will have a designated cardiologist whose primary responsibilities are to confirm the prospective subjects meets the echocardiographic criteria for the study, to ensure the required echocardiograms are performed in accordance with the CIP, and reviewing and approving the site echocardiography eCRFs, if authorized by the PI. Protocol-driven exams should be performed by designated individuals delegated by the site PI. The designated echocardiographer shall also serve as a member of the local Heart Team.

5.5.4 Cardiovascular Imaging Physician

Each site will have a designated cardiovascular imaging specialist, whose responsibilities include ensuring the required pre-TAVR planning MDCT images are acquired per protocol, overseeing the acquisition of the protocol-required cardiac MRI images, analysis of the protocol-required MDCT and MRI exams, and reviewing and approving the site MDCT and MRI eCRFs, if authorized by the PI. The Cardiovascular Imaging Specialist is either a radiologist or cardiologist with expertise in MDCT and Cardiac MRI.

5.5.5 Exercise Testing Physician

Each site will have designated physician whose responsibilities include overseeing the administration, interpretation, and reporting of protocol-required exercise tolerance, and reviewing and approving the site exercise testing eCRFs, if authorized by the PI.

5.5.6 Study Coordinator

Each site will have a designated study coordinator whose responsibilities include coordination of study activities, follow-up evaluations, and maintaining the records defined in the CIP. The study coordinator may conduct follow-up clinical evaluations if qualified per their scope of practice and authorized by the PI.

5.6 Clinical Investigational Agreement and Financial Disclosure

Medtronic contracts with participating institutions/investigators through a clinical investigational agreement that defines the scope and responsibilities and associated compensation related to carrying out the obligations under a clinical study sponsored by Medtronic.

A Clinical Investigational Agreement shall be signed by the participating investigation site and/or the principal investigator at each investigation center per local legal requirements and returned to Medtronic prior to study center activation. The investigator is required to indicate their approval of the CIP (and any subsequent amendments) by signing and dating the agreement. All investigators will be asked to complete financial disclosure statements provided by Medtronic prior to their participation in the study.

5.7 Curriculum Vitae

Current, signed and dated curriculum vitae shall be obtained for all site study personnel, including their current position at the investigation site. The signature on the curriculum vitae must be on or prior to the date of activation or delegation of any tasks.

5.8 Study Site Training and Activation

Prior to investigational center activation or subsequent involvement in study activities, Medtronic will provide training to the investigative team on the clinical investigation plan, relevant standards and regulations, informed consent, data collection and reporting tools, and the study methods, procedures, and requirements. Training may be conducted via site initiation visits, investigator meetings, and/or other media sessions. Medtronic will maintain documentation of these training sessions. If new members join the study team, they will receive training on the applicable study requirements relevant to their role before contributing to the study. Additionally, Medtronic representative(s) may be present at each site's implant procedures as part of the ongoing training process.

Prior to performing study related activities, all regulatory requirements shall be fulfilled, including but not limited to the following:

- IRB/EC approval (and voting list, as required by local law) of the current CIP and ICF
- Fully executed CTA
- Financial disclosure, as applicable
- CV of investigators and investigational site study team members as applicable
- Documentation of delegated tasks

- Documentation of study training
- Additional requirements per local regulations, IRB/EC as applicable

5.9 Eligibility Review Committees

An Eligibility Review Committee (ERC) will be used to ensure subject selection is appropriate and consistent among study sites. The role of the ERC will include the following:

- Confirmation that subjects have severe aortic stenosis per the relevant inclusion/exclusion criteria
- Confirmation that subjects symptoms have been adequately evaluated by the local Heart Team. For subjects unable to undergo ETT, the ERC will confirm if the subject is asymptomatic for AS
- Confirmation that subjects have tricuspid aortic valves and are anatomically suitable for transfemoral TAVR with the study device

The ERC may include representation from the following disciplines: interventional cardiology, cardiac surgery, echocardiography, and heart failure management. A charter that describes the roles, responsibilities, and processes of the ERC will be approved by Medtronic prior to the start of enrollment.

5.10 Echocardiography Core Lab

An Echocardiography Core Lab (ECL) will be used to ensure consistency of evaluation and interpretation of the echocardiographic exams among the study sites. The role of the ECL will include the following:

- Confirming all subjects meet echocardiographic criteria for severity of aortic stenosis and left ventricular function
- Evaluation of all protocol-driven echocardiograms
- Evaluation of unplanned echocardiograms as available

Details on the echocardiography procedures are provided in Section 13.3.

5.11 Clinical Events Committee

A Clinical Events Committee (CEC) will be used to ensure consistent evaluation and adjudication of adverse events and safety-related endpoints. Additional information on the composition, roles, and responsibilities of the CEC is provided in Section 7.7.

5.12 Data Safety Monitoring Board

A Data Safety Monitoring Board (DSMB) will be used to monitor accruing data from study in order to protect the safety of the study subjects. Additional information on the composition, roles, and responsibilities of the DSMB is provided in Section 7.8.

5.13 Publication Committee

A Publication Committee will provide direction and support in the development of clinical publications. The Publication Committee will consist of study investigators and Medtronic representatives. The Publication Committee will be responsible to:

- Define the publication plan

Evolut™ EXPAND TAVR I Feasibility Study Clinical Investigation Plan

D00266108

Revision D

Page 25 of 135

Form

Medtronic

- Review, approve, and prioritize publication proposals
- Provide input on the scientific merit and clinical relevance of ancillary publications
- Identify the manuscript/abstract first author(s)/writer(s)/presenter(s)
- Review publications prior to submission

6. Methods

6.1 Study Population

The study population includes males and females ≥ 65 years of age with severe, asymptomatic AS. Selection criteria are described in Section 6.2.

6.2 Subject Selection Criteria

6.2.1 Inclusion Criteria

Prospective subjects must meet all of following inclusion criteria to be eligible for implantation:

1. Severe aortic stenosis, defined as:
 - $AVA \leq 1.0 \text{ cm}^2$, or $AVA_I \leq 0.6 \text{ cm}^2/\text{m}^2$, **and**
 - Mean gradient $\geq 40 \text{ mmHg}$ **or** $V_{\text{max}} \geq 4.0 \text{ m/sec}$
2. NYHA I
3. Subject denies symptoms attributable to aortic stenosis, including but not limited to:
 - Dyspnea on rest or exertion
 - Angina
 - Syncope in the absence of another identifiable cause
 - Fatigue
4. LVEF $\geq 50\%$
5. Anatomically suitable for transfemoral TAVR using the Medtronic Evolut PRO+ system
6. The subject and treating physician agree the subject will return for all required follow-up visits

6.2.2 Exclusion Criteria

If any of the following exclusion criteria are present, the prospective subject is not eligible for implantation:

1. Age < 65 years
2. Class I indication for cardiac surgery
3. Very severe aortic stenosis, defined as $V_{\text{max}} \geq 5 \text{ m/sec}$, or mean gradient $\geq 60 \text{ mmHg}$
4. Bicuspid, unicuspid, or quadracuspid aortic valve
5. Contraindication for placement of a bioprosthetic valve
6. A known hypersensitivity or contraindication to any of the following that cannot be adequately pre-medicated:
 - Aspirin, heparin, or bivalirudin
 - Ticlopidine and clopidogrel
 - Nitinol (titanium or nickel)
 - Contrast media

7. Blood dyscrasias as defined: leukopenia (WBC < 1000 mm³), thrombocytopenia (platelet count <50,000 cells/mm³), history of bleeding diathesis or coagulopathy, or hypercoagulable states
8. Ongoing sepsis, including active endocarditis
9. Any percutaneous coronary or peripheral interventional procedure within 30 days prior to date of qualifying echocardiogram
10. In need of and suitable for coronary revascularization per Heart Team
11. Chronic obstructive pulmonary disease (GOLD stage 3 or higher)⁵⁷
12. Placement of cardiac resynchronization device within 90 days of qualifying echocardiogram
13. Symptomatic carotid or vertebral artery disease or successful treatment of carotid stenosis within 70 days of qualifying echocardiogram
14. Heart failure event or hospitalization within 14 days prior to qualifying echocardiogram
15. Cardiogenic shock manifested by low cardiac output, vasopressor dependence, or mechanical hemodynamic support
16. Recent (within 60 days of qualifying echocardiogram) cerebrovascular accident (CVA) or transient ischemic attack (TIA)
17. Child-Pugh class C liver cirrhosis
18. Gastrointestinal (GI) bleeding that would preclude anticoagulation
19. Subject refuses a blood transfusion
20. Severe dementia (resulting in either inability to provide informed consent for the study/procedure, prevents independent lifestyle outside of a chronic care facility, or will fundamentally complicate rehabilitation from the procedure or compliance with follow-up visits)
21. Estimated life expectancy of less than 24 months due to associated non-cardiac co-morbid conditions
22. Other medical, social, or psychological conditions that in the opinion of the investigator precludes the subject from appropriate consent or adherence to the protocol required follow-up exams
23. Currently participating in an investigational drug or another device trial or study (excluding registries)
24. Evidence of an acute myocardial infarction ≤ 30 days before date of qualifying echocardiogram⁵⁸
25. Advanced renal impairment (defined as GFR <30 mL/min) or need for renal replacement therapy
26. Need for emergency surgery for any reason
27. Subject is pregnant or breast feeding
28. Subject is less than legal age of consent, unable to provide his/her own informed consent, legally incompetent, or otherwise vulnerable

Anatomical exclusion criteria:

29. Pre-existing prosthetic heart valve in any position
30. Severe mitral regurgitation
31. Severe tricuspid regurgitation
32. Moderate or severe mitral stenosis
33. Hypertrophic obstructive cardiomyopathy
34. Significant aortopathy requiring ascending aortic replacement

35. Severe aortic regurgitation

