6.5 Screening and Enrollment

The process of patient screening and subject enrollment is as follows (Figure 2):

1. Patients identified by or presented to the study site with AS will be screened by the investigative team for the subject selection criteria using available medical records, including relevant imaging studies previously performed for diagnostic purposes.
2. If the patient is deemed a potential candidate, all aspects of the study will be explained to the patient. The patient will then be invited to participate in the study. If the patient agrees to participate, written informed consent will be obtained. The date informed consent is signed is considered the point of enrollment, and the subject will be assigned a Subject ID number.
3. The subject will undergo transthoracic echocardiography (TTE) to assess his/her degree of AS and cardiac function.
4. If the site investigative team determines the subject meets AS criteria for severe asymptomatic AS, the qualifying echocardiogram will be submitted to the ECL for confirmation of severity of AS and other echocardiographic criteria.
5. If the ECL confirms echocardiographic criteria are met¹, the subject will undergo the following evaluations:
 - Exercise tolerance testing (ETT), unless contra-indicated
 - Multi-detector computed tomography (MDCT)
 - Pulmonary function testing (simple spirometry with FEV₁)
 - Cardiac MRI
 - Coronary arteriography if there is uncertainty regarding the status of coronary artery disease
6. If the local Heart Team considers the subject suitable for implantation, the following information should be submitted to the ERC:
 - Clinical assessments including medical history, co-morbidities, and symptomology
 - TTE data on degree of AS and cardiac function
 - MDCT data on anatomical suitability
7. The ERC will review the submitted information and either confirm, disapprove, or defer eligibility for implantation. Subjects confirmed eligible for implantation should undergo TAVR within 90 days of ERC approval. Subjects disapproved should be exited from the study, and not be reconsidered for future participation without permission from Medtronic.

¹If a subject has balloon aortic valvuloplasty after their qualifying TTE, they must have repeat TTE to confirm he/she meets criteria for aortic stenosis prior to submission to the ERC.

[figure not shown]

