6.6 Required Evaluations

Protocol required evaluations should be performed at the study site. The protocol required evaluations are as follows and summarized in Table 1. Additional information on data collection requirements is provided in Section 6.13 through Section 6.18. As this is an interventional study, some or all of the required study procedures may be outside of standard of care for a given patient.

Baseline (within 12 weeks prior to submission to the Eligibility Review Committee²)

- Clinical assessment and medical history, including NYHA classification
- Coronary arteriography (may be either selective or by computed tomography)
- Transthoracic echo (TTE)
- Exercise Tolerance Test (ETT)³
- Cardiac MRI
- Simple spirometry (timed vital capacity with FEV₁)
- MDCT (peripheral vasculature and aortic annulus)
- 12-lead ECG
- Complete blood count
- pro B-type natriuretic peptide (NT-proBNP)
- Heart Team assessment
- Six-minute walk test (6MWT)
- Modified Rankin Score
- Quality of Life Questionnaires:
 - Kansas City Cardiomyopathy Questionnaire (KCCQ)
 - European Quality of Life – 5 Dimensions (EQ-5D)
- Medications
- Adverse events

Implant Procedure

- Pre-deployment hemodynamics (LV and aortic pressures)
- Aortography (final result)
- Adverse events and device deficiencies

Discharge

- Clinical assessment (NYHA not assessed at discharge)
- 12 lead ECG
- Medications
- TTE⁴
- Adverse events and device deficiencies

30 days (between 30 to 45 days post implant)

² Pre-implant MDCT and coronary arteriography should be performed within 365 days of submission to the eligibility review committee

³ Unless subject has contra-indication for ETT

⁴ Discharge TTE should be performed ≥ 12 hours and ≤ 7 days post procedure

- Clinical assessment, including NYHA classification
- 12 lead ECG
- TTE
- Medications
- Adverse events and device deficiencies
- KCCQ

6 Months (between 183 to 210 days post implant)

- Clinical assessment, including NYHA classification
- 12 lead ECG
- TTE
- Medications
- pro B-type natriuretic peptide (NT-proBNP)
- Quality of Life Questionnaires:
 - Kansas City Cardiomyopathy Questionnaire (KCCQ)
 - European Quality of Life – 5 Dimensions (EQ-5D)
- Cardiac MRI
- Six-minute walk test (6MWT)
- Adverse events and device deficiencies

1 Year (between 365 to 395 days post implant)

- Clinical assessment, including NYHA classification
- TTE
- Medications
- KCCQ
- Adverse events and device deficiencies

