2 Years (between 730 to 760 days post implant)

- Clinical assessment, including NYHA classification
- TTE
- Medications
- KCCQ
- Adverse events and device deficiencies

3 Years (between 1095 to 1125 days post implant)

- Clinical assessment, including NYHA classification
- TTE
- Medications
- KCCQ
- Adverse events and device deficiencies

4 Years (between 1460 to 1490 days post implant)

- Clinical assessment, including NYHA classification
- TTE
- Medications

- KCCQ
- Adverse events and device deficiencies

5 Years (between 1825 to 1855 days post implant)

- Clinical assessment, including NYHA classification
- TTE
- Medications
- KCCQ
- Adverse events and device deficiencies

Other Evaluations

- Suspected stroke events should be confirmed by neurology consult and neuroimaging per site’s standard practice. A Modified Rankin Score assessment should be conducted at 1 and 3 months following any confirmed stroke event.
- The investigative team should follow their standard practices for assessment of suspected myocardial infarction, acute kidney injury, neurological events, prosthetic valve endocarditis, prosthetic valve thrombosis, etc.
- Non-protocol echocardiograms (e.g. performed for suspicion of prosthetic valve dysfunction) should be submitted to the ECL for evaluation.

Table 1. Summary of required evaluations and visit schedule

	Baseline	Implant	Discharge	30 Days	6 Months	Annual through 5 Years	1 month post stroke event	3 months post stroke event
Clinical assessment including NYHA	✓ ⁵		✓ ¹	✓	✓	✓		
Transthoracic Echo	✓		✓ ⁴	✓	✓	✓		
Multi-detector CT	✓							
12-lead ECG	✓		✓	✓	✓			
Coronary arteriography	✓							
Exercise Tolerance Test (unless contraindicated)	✓							
Cardiac MRI	✓				✓			
6-Minute Walk Test	✓				✓			
Spirometry	✓							
Complete Blood Count	✓							
Pro B-type natriuretic peptide	✓				✓			

Heart Team Assessment	✓							
Aortography		✓						
Hemodynamics		✓						
Medications	✓		✓	✓	✓	✓		
KCCQ	✓			✓	✓	✓		
EQ-5D	✓				✓			
Modified Rankin Score	✓						✓	✓
Adverse Events and/or device deficiencies ²	✓	✓	✓	✓	✓	✓		

Notes

1. NYHA not required at discharge
2. Adverse events should be assessed and captured at each follow-up visit after time of informed consent.
3. Discharge TTE used for “Device Success” should be performed > 12 hours and ≤ 7 days post implant
4. Clinical assessment and medical history required at baseline

Visit Windows

Baseline	Within 12 weeks prior to submission to ERC (except for MDCT and coronary arteriography)

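### The PCI, MI and heart failure look-back exclusions stop at the qualifying echo, so they do not cover the interval from echo to TAVR (at most 174 days plus ERC review time), and no eligibility re-check before implant is stated

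*Protocol*

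**What the plan says.** Protocol 6.2.2 opens by stating that a subject with any listed exclusion may not be implanted. Three of the exclusions count only events before the qualifying echo:

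- Exclusion 9: "Any percutaneous coronary or peripheral interventional procedure within 30 days prior to date of qualifying echocardiogram".
- Exclusion 14: "Heart failure event or hospitalization within 14 days prior to qualifying echocardiogram".
- Exclusion 24: "Evidence of an acute myocardial infarction ≤ 30 days before date of qualifying echocardiogram".

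Three more are tied to the same echo with no direction given: 12 (cardiac resynchronization device, 90 days), 13 (treated carotid stenosis, 70 days) and 16 (CVA or TIA, 60 days).

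The echo comes early. In Protocol 6.5 it is step 3, ahead of core lab confirmation, exercise testing, CT, the Heart Team and the ERC. Protocol 6.6 sets the baseline window as "within 12 weeks prior to submission to the Eligibility Review Committee". Step 7 of 6.5 then says "Subjects confirmed eligible for implantation should undergo TAVR within 90 days of ERC approval".

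The Implant visit in 6.6 and Table 1 lists hemodynamics, aortography, and adverse events and device deficiencies. It has no NYHA class, symptom review or eligibility confirmation. The one rule for an event after the echo is the footnote to 6.5: a repeat TTE after balloon valvuloplasty, to be done before ERC submission.

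**The concern.** The criteria decide eligibility for one date, the implant, but are counted from another. An event shortly before the echo excludes a subject. The same event after the echo, and so nearer to the procedure, does not trigger the same criterion. It would not be a protocol deviation under 6.10 either, because exclusions 9, 14 and 24 would not have been breached.

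Two things are at stake. The first is safety: a subject could be implanted as eligible soon after an event that the sponsor evidently wanted kept at a distance. The second is what the study is meant to deliver. A primary objective (Protocol 4.1) is to estimate event rates for pivotal studies, and complications that follow from a recent coronary or cerebral event would enter the 30-day rates. Baseline echo, KCCQ, 6MWT and NT-proBNP may also predate the intervening event, so the 6-month changes could mix its effect with that of TAVR.

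**Working it through.** The documents state no echo-to-TAVR interval, so there is no figure of the plan's own to reproduce. It has to be built from the two stated windows.

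**Inputs**

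- Echo to ERC submission: at most 12 weeks, so 12 × 7 = 84 days (Protocol 6.6). The visit-window list under Table 1 confirms that the echo is not exempt: "Within 12 weeks prior to submission to ERC (except for MDCT and coronary arteriography".
- ERC submission to approval: no limit stated. Call it r; 0 to 30 days is assumed here.
- ERC approval to TAVR: 90 days (Protocol 6.5, step 7), worded as a recommendation.

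**Interval**

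Echo to TAVR = 84 + r + 90 = 174 + r days at the limits.

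- r = 0: 174
- r = 7: 181
- r = 14: 188
- r = 30: 204

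**Coverage at r = 0, with day 0 as TAVR and the echo on day −174**

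| Exclusion | Event | Window | Days covered | Last days before TAVR not covered |
|---|---|---|---|---|
| 9 | PCI or peripheral procedure | 30 days before echo | −204 to −174 | 174 |
| 24 | MI | 30 days before echo | −204 to −174 | 174 |
| 14 | Heart failure event | 14 days before echo | −188 to −174 | 174 |
| 16 | CVA or TIA | 60 days, read two-sided | up to −114 | 174 − 60 = 114 |
| 13 | Treated carotid stenosis | 70 days, read two-sided | up to −104 | 174 − 70 = 104 |
| 12 | Resynchronization device | 90 days, read two-sided | up to −84 | 174 − 90 = 84 |

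Each figure in the last column rises by r. If 12, 13 and 16 are read as backward only, their figure is also 174.

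For 9, 14 and 24 the gap does not depend on the maxima. It equals whatever the echo-to-TAVR interval is. For 16, 13 and 12 read two-sided, a gap opens only when that interval exceeds 60, 70 or 90 days.

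**What else could catch an event after the echo**

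Inclusion criteria 2 (NYHA I), 3 (denies symptoms) and 4 (LVEF at least 50%) carry no echo date. Nor do exclusions 2 (Class I indication for cardiac surgery), 10 (in need of and suitable for revascularization), 15 (cardiogenic shock) and 26 (need for emergency surgery).

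- Heart failure event: the definitions in Protocol 13.8.3 require new or worsening symptoms, so it would ordinarily conflict with inclusion 2 or 3.
- MI: exclusion 10 or 15, or the angina item, may apply while it is active. Once the subject has recovered, none clearly does.
- Stroke or TIA: none of these criteria names it.
- Completed PCI: exclusion 10 may no longer apply once the vessel has been treated, and no other listed criterion clearly does.

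**Scale of one event**

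With 75 subjects, one event moves a 30-day rate by about 1/75 = 1.3 percentage points. That is true of any single event. It shows how sensitive the rates are, not how often this would happen.

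**The case against.** The strongest reply is that the protocol has other safeguards, and much of it stands. A reader might infer that an MI, PCI or heart failure event just before implant would exclude nobody. The documents do not support that. NYHA I, denial of symptoms and the undated exclusions all govern eligibility for implantation, and Protocol 6.10 lists implanting a subject who fails a criterion as a deviation. The Heart Team and the ERC review history and symptoms after the echo, and the ERC may defer or disapprove. Adverse events are collected from consent, and serious ones reach the sponsor within 72 hours (Protocol 7.4).

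A reader might also infer that a PCI prompted by the study's own arteriography could never meet exclusion 9, because that test comes at step 5, after the echo. This is too strong as well. Step 5 is conditional ("Coronary arteriography if there is uncertainty regarding the status of coronary artery disease"), a footnote in 6.6 allows arteriography up to 365 days before ERC submission, and tests done before consent may be used. Arteriography may therefore precede the echo. A PCI at step 5 is one possible route, not every case. Nor do all six exclusions look backward: 12, 13 and 16 give no direction.

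It is also fair to say that 174 days adds two maxima, that no event frequency is available, and that an event before day 0 is not itself counted in the 30-day rates.

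What remains is narrower. Heart Team and ERC review end at approval, and up to 90 days may follow. An adverse event report would make the sponsor aware of an intervening MI or stroke, but nothing links that report to eligibility. The undated criteria still apply on paper, yet no visit is assigned to check them. The balloon valvuloplasty footnote shows that the sponsor accepts that an event after the echo can undo qualification, but it covers one event and stops at ERC submission.

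**Conclusion.** The concern holds in a limited form. Exclusions 9, 14 and 24 leave the whole echo-to-TAVR interval uncovered, and exclusions 12, 13 and 16 are ambiguous about direction. At the stated limits the uncovered period is 174 days plus ERC review time for 9, 14 and 24. For 16, 13 and 12 read two-sided it is 114, 104 and 84 days, plus the same review time. These are maxima. They assume that the echo is as old as allowed at submission and that TAVR takes place on day 90 after approval.

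The practical gap is a completed PCI, or a recovered MI, stroke or TIA, between echo and procedure. Most heart failure events and some MIs would meet another criterion, provided someone checks, and no check after ERC approval is stated. The number of subjects affected cannot be estimated from the documents. The case for a change rests on its low cost and on the sensitivity of rates from 75 subjects, not on a demonstrated frequency.

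**What to change.** 1. In Protocol 6.2.2, reconcile the echo anchor of exclusions 9, 12, 13, 14, 16 and 24 with the section's stated purpose of deciding eligibility for implantation. State the direction for 12, 13 and 16. The choice of anchor and intervals is the sponsor's.
2. In the Implant visit of 6.6 and Table 1, add a confirmation from history that the existing inclusion and exclusion criteria are still met and that no MI, PCI, CVA/TIA or heart failure event has occurred since the qualifying echo. The sponsor defines what follows if it is not met.
3. Reconcile the balloon valvuloplasty footnote in 6.5, which ends at ERC submission, with the period up to the procedure.

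The cost is protocol wording, one short form before the procedure, and a few subjects deferred after approval. No new test is needed.
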